3.4 Concomitant Treatments

3.4.1 **Prohibited and/or Restricted Treatments**

Once enrolled, subjects may not receive any of the following for the duration of both screening and treatment periods:

- Antihyperglycemic medication (other than protocol required medication and/or protocol-allowed open-label rescue medication).
- Stable weight loss medication is allowed.
- Treatment with any stable replacement or chronic corticosteroid therapy at the time of screening is permitted. During the trial (beginning with screening), new initiation of treatment with any systemic corticosteroid therapy that will involve ≥ 5 days of therapy is prohibited (inhaled and topical are allowed). The medical monitor should be consulted prior to beginning therapy with corticosteroids for subjects who require acute systemic corticosteroid treatment.
- In countries where dose adjustment would be required by the local saxagliptin label: if initiation of treatment with any potent cytochrome P450 3A4/5 inhibitors during the trial is required, the medical monitor should be consulted prior to beginning therapy with any potent cytochrome P450 3A4/5 inhibitors.

3.4.2 Other Restrictions and Precautions

- Subjects must comply with their prescribed dosing regimen to preserve study integrity and ensure subject safety.
- Subjects should be cautioned that any new prescription, over-the-counter or herbal/nutritional therapies should be discussed thoroughly with the Investigator as concomitant use could result in alterations to their glycemic control and may place them at risk for significant hypoglycemic episodes.
- Subjects must make every attempt to adhere to the diet and exercise counseling (see Section 5.9.1) and to the protocol visit schedule (see Section 5.1).
- Women of child-bearing potential must immediately contact the Investigator if they suspect they might be pregnant and if they have changed or plan to change their birth control method (see Section 6.4).

3.5 Discontinuation of Subjects from Treatment

Subjects MUST discontinue investigational product (and noninvestigational product at the discretion of the investigator) for any of the following reasons:

- Withdrawal of informed consent (subject's decision to withdraw for any reason)
- Any clinical adverse event (AE), laboratory abnormality or intercurrent illness which, in the opinion of the investigator, indicates that continued participation in the study is not in the best interest of the subject
- Pregnancy
- Termination of the study by Bristol-Myers Squibb (BMS)
- Loss of ability to freely provide consent through imprisonment or involuntary incarceration for treatment of either a psychiatric or physical (eg, infectious disease) illness
- $eGFR < 60 \text{ mL/min/}1.73 \text{m}^2$ for sustained period of time (12 16 weeks)

Dapaglifozin based on its mechanism of action has been shown to reduce eGFR by up to 10% with initiation of therapy; however this has in general been reversible and not resulted in renal failure and eGFR values returned to baseline within 12 - 24 weeks of continued therapy.

In case of a decision to discontinue treatment the Investigator will follow the subject until the event has resolved or stabilized, however at least till week 24.

All subjects who discontinue from treatment should comply with protocol specified follow-up procedures as outlined in Section 5. The only exception to this requirement is when a subject withdraws consent for all study procedures or loses the ability to consent freely (ie, is imprisoned or involuntarily incarcerated for the treatment of either a psychiatric or physical illness).

If a subject was withdrawn before completing the study, the reason for withdrawal must be entered on the appropriate case report form (CRF) page.

In addition, subjects who prematurely discontinue from the study may be contacted, after discontinuation from the study, to collect vital status information.

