[figure not shown]

Clinical Protocol CV181169

A Multicenter, Randomized, Double-Blind, Active-Controlled, Parallel Group, Phase 3 Trial to Evaluate the Safety and Efficacy of Add-On Therapy with Saxagliptin and Dapagliflozin added to Metformin compared to Add-On Therapy with Saxagliptin in combination with Metformin or Dapagliflozin in combination with Metformin in Subjects with Type 2 Diabetes who have Inadequate Glycemic Control on Metformin Alone

This document is the confidential and proprietary information of Bristol-Myers Squibb Company and its global affiliates (BMS). By reviewing this document, you agree to keep it confidential and to use and disclose it solely for the purpose of assessing whether your organization will participate in and/or the performance of the proposed BMS-sponsored study. Any permitted disclosures will be made only on a confidential "need to know" basis within your organization or to your independent ethics committee(s). Any other use, copying, disclosure or dissemination of this information is strictly prohibited unless expressly authorized in writing by BMS. Any supplemental information (e.g., amendments) that may be added to this document is also confidential and proprietary to BMS and must be kept in confidence in the same manner as the contents of this document. Any person who receives this document without due authorization from BMS is requested to return it to BMS or promptly destroy it. All other rights reserved. Saxagliptin and Dapagliflozin and

DOCUMENT HISTORY

Document	Date of Issue		Summary of Change
Original Protocol		Not applicable	

SYNOPSIS

Clinical Protocol CV181169

Title of Study: A Multicenter, Randomized, Double-Blind, Active-Controlled, Parallel Group, Phase 3 Trial to Evaluate the Safety and Efficacy of Add-On Therapy with Saxagliptin and Dapagliflozin added to Metformin compared to Add-On Therapy with Saxagliptin in combination with Metformin or Dapagliflozin in combination with Metformin in Subjects with Type 2 Diabetes who have Inadequate Glycemic Control on Metformin Alone

Investigational Product(s), Dose and Mode of Administration, Duration of Treatment with Investigational Product(s):

Saxagliptin 5 mg, administered orally once daily for the 24-week double-blind treatment period.

Dapagliflozin 10 mg tablets, administered orally once daily for the 24-week double-blind treatment period.

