Metformin XR 1500 - 2000 mg, administered orally once daily for the 4 week lead-in and the 24-week double-blind treatment period

Study Phase: Phase 3

Research Hypothesis:

A combination of saxagliptin and dapagliflozin added concurrently to metformin is superior to saxagliptin or dapagliflozin added to metformin in reducing HbA1c.

Primary Objective:

To compare the mean change from baseline in glycosylated hemoglobin (HbA1c) achieved with concurrent addition of saxagliptin and dapagliflozin to metformin versus (vs.) the addition of placebo and saxagliptin to metformin and vs. the addition of placebo plus dapagliflozin to metformin after 24 weeks of double-blind treatment.

Secondary Objectives:

- To compare the mean change from baseline achieved with concurrent addition of saxagliptin and dapagliflozin to metformin vs. the addition of placebo and saxagliptin to metformin and vs. the addition of placebo plus dapagliflozin to metformin after 24 weeks of double-blind treatment in:
 - 1. 2-hour post prandial glucose from a liquid meal tolerance test (2-h MTT)
 - 2. Fasting plasma glucose (FPG)
- To compare the proportion of subjects achieving therapeutic glycemic response, defined as HbA1c < 7.0%, after 24 weeks of double-blind treatment with concurrent addition of saxagliptin and dapagliflozin to metformin vs. the addition placebo and saxagliptin to metformin and vs. the addition of placebo plus dapagliflozin to metformin.
- To compare the mean change in total body weight achieved with the addition of saxagliptin and dapagliflozin to metformin vs. the addition of placebo and saxagliptin to metformin.

Other Objectives:

• To compare the percent of subjects who require glycemic rescue or discontinue study treatment for lack of efficacy with concurrent addition of saxagliptin and dapagliflozin to metformin vs. the addition

Saxagliptin and Dapagliflozin	CV181169
and	Clinical Protocol

of placebo and saxagliptin to metformin and vs. the addition of placebo plus dapagliflozin to metformin after up to 24 weeks of double-blind treatment.

[figure not shown]
- To compare the time to glycemic rescue or discontinuation for lack of efficacy with concurrent addition of saxagliptin and dapagliflozin to metformin vs. the addition of placebo and saxagliptin to metformin and vs. the addition of placebo plus dapagliflozin to metformin after up to 24 weeks of double-blind treatment.

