Both metformin and saxagliptin are widely used anti-diabetic treatments. Metformin will be prescribed according to its approved label. The potential risks associated with dapagliflozin have been identified based upon the mechanism of action, the preclinical results, and the extensive clinical experience to date, including a study combining it with another DPP4-inhibitor and / or metformin. Thus, the benefits and risks associated with the investigational drugs and metformin, are well established and presented in their approved prescribing information and investigator brochure respectively. No study procedure will put patients at a risk beyond those ordinarily encountered during the performance of routine medical examinations or tests.

Protection against risks

The present study has been designed with appropriate measures in place so as to monitor and minimize any of the potential health risks to participating patients. In order to ensure safety of all patients participating in this study, the AstraZeneca and Bristol-Myers Squibb will conduct a real-time review of all safety information from all ongoing clinical saxagliptin and dapagliflozin studies as they become available. Safety signal detection will include the integration of all available sources of safety information, including clinical study data, adverse event reports, pre-clinical data, epidemiological studies and literature reports, to identify and characterize unrecognized safety risks or changes in those which are currently expected Adverse Drug Reactions. Any information that may affect the benefit-risk profile of saxagliptin and dapagliflozin will be immediately communicated to relevant Health Authorities and appropriate actions will be taken regarding the clinical program as needed. In addition, all studies which include dapagliflozin are subject to a carefully designed patient risk management plan that includes the temporary and if necessary permanent discontinuation of investigational product in individual patients in whom a potential health risk or a laboratory abnormality of clinical concern has been identified. Investigators are also provided guidance on appropriate management of potential risks such as hypoglycemia, urinary tract infections and decreased renal function and also the potential risks of saxagliptin mentioned in the Risk Management Plan.

Potential benefits to patients

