Subjects should not be discontinued from any treatment phase based on single episodes of hypoglycemia or symptoms of hypoglycemia unless clinically indicated. The assessment of a single fingerstick or central laboratory glucose value should not be the sole assessment used to determine subject discontinuation due to hypoglycemia.

Clinical indications for discontinuation due to hypoglycemia may include the following:

- Multiple occasions of episodes outlined below that, in the opinion of the Investigator, indicate that continued treatment with study therapy is not in the best interest of the subject. This includes, but is not limited to:
 - Symptoms suggestive of hypoglycemia (eg, sweating, shakiness, increased heart rate, confusion, dizziness, lightheadedness, or hunger) in the absence of environmental factors known to contribute to hypoglycemia (ie, excess physical activity, concurrent illness, or missed or delayed meal) and/or
 - Documented fingerstick glucose values $\leq 54 \text{ mg/dL}$ ($\leq 3.1 \text{ mmol/L}$).
- A subject may also be discontinued from the study due to severe hypoglycemia as determined by the Investigator.

Down titration of blinded study drug and/or background antihyperglycemic agent will not be allowed at any time during the study.

Saxagliptin and Dapagliflozin	CV181169
and	Clinical Protocol

If fingerstick glucose values are discordant from glycemic control assessed by the central laboratory or with clinical symptoms, the subject's glucose meter should be tested and the procedure for using it reviewed with the subject.

Section 5.3.1.1 provides additional guidance on management and reporting of hypoglycemia.

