4.1.1 Investigational Product

An investigational product, also known as investigational medicinal product in some regions, is defined as follows:

A pharmaceutical form of an active substance or placebo being tested or used as a reference in a clinical study, including products already with a marketing authorization but used or assembled (formulated or packaged) in a way different from the authorized form, or used for an unauthorized indication, or when used to gain further information about the authorized form.

In this protocol, investigational products (also described in Table 4.1) are: Dapagliflozin 10 mg and matching placebo tablets, saxagliptin 5 mg and matching placebo tablets, and metformin XR 500 mg tablets

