4.3 Selection and Timing of Dose for Each Subject

Blinded Study Medication

Saxagliptin 5 mg tablets and matching placebo tablets, administered orally once daily for the 24-week double-blind treatment period. Saxagliptin 5 mg is the maximum

recommend daily dose as well as the usual daily dose. It is not currently labeled for triple therapy use in combination with dapagliflozin and metformin.

Dapagliflozin 10 mg tablets and matching placebo tablets administered orally once daily for the 24-week double-blind treatment period.

Dapagliflozin 10 mg is an investigational drug. Based on considerations of efficacy, pharmacodynamic, and safety data from the Phase 1 and 2 programs, daily doses up to 10mg of dapagliflozin have been chosen for the Phase 3 studies. The 10 mg dose was chosen for this study as it has been extensively studied in Phase 3 trials and is the dose expected to deliver the most favorable benefit:risk profile.

Open Label Metformin

Subjects entering the study on metformin IR will be switched to open-label metformin XR 500 mg tablets administered orally once daily with food at doses \geq 1500 mg/day from the 4-week lead-in period. Subjects whose current therapy is not based on 500 mg metformin IR tablets will have their dose modified as noted in Appendix 4 and for the 24-week double-blind treatment period.

Subjects entering the study on metformin XR, whose current therapy is not based on 500 mg metformin XR tablets, will have their dose modified as noted in Appendix 4 for the lead-in period and for the 24-week double-blind treatment period.

Subjects must be receiving metformin in accordance with the product label for their country.

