6.4 Pregnancy

If, following initiation of the investigational product, it is subsequently discovered that a study subject is pregnant or may have been pregnant at the time of investigational product exposure, including during at least 6 half lives after product administration, the investigational product will be permanently discontinued in an appropriate manner (eg, dose tapering if necessary for subject safety). Protocol-required procedures for study discontinuation and follow-up must be performed on the subject unless contraindicated by pregnancy (eg, x-ray studies). Other appropriate pregnancy follow-up procedures should be considered if indicated.

The investigator must immediately notify the BMS (or designee) Medical Monitor of this event and complete and forward a Pregnancy Surveillance Form to BMS (or designee) within 24 hours and in accordance with SAE reporting procedures described in Section 6.1.1.

Follow-up information regarding the course of the pregnancy, including perinatal and neonatal outcome and, where applicable, offspring information must be reported on the Pregnancy Surveillance Form.

Any pregnancy that occurs in a female partner of a male study participant should be reported to the sponsor. Information on this pregnancy will be collected on the Pregnancy Surveillance Form.

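### Because metformin XR is classed as investigational product, the mandatory stop in 3.5 and 6.4 literally takes background metformin away with the blinded tablets

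*Protocol*

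**What the plan says.** Section 4.1.1 lists the investigational products. After dapagliflozin 10 mg and its placebo come "saxagliptin 5 mg and matching placebo tablets, and metformin XR 500 mg tablets". The synopsis does the same: under its investigational-product heading the third entry reads "Metformin XR 1500 - 2000 mg, administered orally once daily for the 4 week lead-in and the 24-week double-blind treatment period". Section 4.1.2 describes noninvestigational product in general terms, including standard-of-care medication, but the only therapy it goes on to name is rescue medication.

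The stop rule in 3.5 is built on that classification: "Subjects MUST discontinue investigational product (and noninvestigational product at the discretion of the investigator) for any of the following reasons". Six reasons follow. Section 6.4 adds that in pregnancy "the investigational product will be permanently discontinued in an appropriate manner".

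Other sections speak of metformin as something apart. Section 1.5 says that "the benefits and risks associated with the investigational drugs and metformin, are well established". Section 3.5.2, on down-titration, refers to "blinded study drug and/or background antihyperglycemic agent". Section 4.3 handles the drug under its own open-label heading: "Subjects entering the study on metformin IR will be switched to open-label metformin XR 500 mg tablets administered orally once daily with food".

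Stopping treatment is not leaving the study. Section 3.5 requires follow-up to at least Week 24, and 5.3.8.1 keeps subjects who stop study drug on the regular visit schedule.

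**The concern.** Subjects entered with a screening HbA1c of 8.0 to 12.0% while already taking at least 1500 mg of metformin a day. Suppose one of them develops a problem tied to a blinded tablet, such as a genital infection, which 1.4 names as a dapagliflozin risk, and the investigator judges that continuing is not in the subject's interest. The sensible action is to stop the blinded tablets and leave stable metformin alone. By the letter of 3.5 the study metformin, 1500 to 2000 mg a day, must stop as well.

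A site that keeps metformin going departs from a mandatory instruction, and a site that obeys withdraws a drug that had no part in the event. Sites may therefore act differently in the same situation. What is at stake is the care of subjects who have stopped treatment and uniform conduct across sites.

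**Working it through.** The point turns on text, so the check sets the definition, the rule and any exemption side by side.

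1. **Definition.** By 4.1.1 and the synopsis, metformin XR is investigational product. Section 4.1.2 does not name it as noninvestigational.

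2. **Rule.** Under 3.5, stopping investigational product is mandatory and stopping noninvestigational product is discretionary. Putting step 1 into this rule makes stopping metformin XR mandatory. The discretion clause, which would naturally protect background therapy, reaches rescue medication but not metformin. Section 6.4 uses the same term and gives the same result for pregnancy.

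3. **Exemption.** Sections 1.5, 3.5.2 and 4.3 show that metformin was thought of as background therapy. None of them changes the definition or the stop rule.

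4. **Which triggers matter.** All six apply literally. Sorting them by whether the subject stays under follow-up and whether the reason itself bears on metformin gives:

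| Trigger in 3.5 | Followed afterwards? | Mainly affected? |
|---|---|---|
| Consent withdrawn | Largely not | No |
| Adverse event, laboratory abnormality or illness, in the investigator's opinion | Yes | Yes: the reason may concern only a blinded tablet |
| Pregnancy | Yes | Yes: the local label should decide on metformin |
| Study terminated by the sponsor | Largely not | No |
| Imprisonment or involuntary detention | No, exempted in 3.5 | No |
| Sustained eGFR below 60 | Yes | No: this can itself justify stopping metformin, which 1.4 ties to creatinine limits |

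That leaves 2 of 6. The sorting is a clinical judgement.

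5. **Therapy after the stop.** Section 3.4.1 restricts other antihyperglycemic drugs during the screening and treatment periods and exempts protocol-required medication and allowed rescue. The rescue rules in 3.5.1 are written as an addition to the blinded regimen, and the permitted rescue agents exclude metformin. If the treatment period has ended for the subject, the 3.4.1 restriction arguably lapses. If it has not, metformin is arguably protocol-required. The text does not settle which.

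6. **Scale.** Follow-up remaining after a stop is 24 − 0 = 24 weeks from Day 1, 24 − 6 = 18 from Week 6, 24 − 12 = 12 from Week 12 and 24 − 18 = 6 from Week 18. The planned enrolment in 8.1 reproduces: 163 / 0.95 = 171.6, rounded up to 172 per arm, and 3 × 172 = 516. Each 1% of subjects who stop is 0.01 × 516 = 5.16 people. These figures give exposure time and a denominator. They do not estimate an effect, because the protocol states no discontinuation rate.

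**The case against.** The context makes the intention clear. With 1.5, 3.5.2 and 4.3 in front of them, many investigators would read 3.5 as meaning the blinded tablets. The adverse-event trigger also depends on the investigator's opinion that participation should not continue, so an infection alone does not set it off; 5.3.2.1 asks only for withholding study drug during an upper urinary tract infection. Safeguards exist too: scheduled visits with FPG, recommended daily self-monitoring (5.3.1), unscheduled visits (5.3.8.2), emergency unblinding (4.4) and the immediate-hazard provision (9.1.1). Classing sponsor-supplied metformin as investigational may be deliberate, for drug accountability.

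Most of this stands, and it keeps the point minor. It does not remove the point. Once the trigger is met, 3.5 offers no product-by-product choice, and the safeguards limit harm without correcting the instruction. Accountability can be kept by leaving 4.1.1 alone.

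Three stronger readings are tempting and should not be drawn:

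- *Metformin must stop whatever the reason.* The rule covers the reasons listed in 3.5, and pregnancy in 6.4. Stopping for hypoglycemia under 3.5.2 is discretionary.
- *The subject loses all metformin, or all glucose-lowering therapy, until Week 24.* The rule stops a trial product. No sentence forbids ordinary prescribed metformin afterwards, and 3.4.1 is ambiguous on the question.
- *The primary comparison is biased.* Section 8.4.2.1 uses observations before rescue and states no exclusion after discontinuation, so HbA1c measured after a metformin stop could enter the model. But the same rule applies in all three arms, no stop rates are given by arm, and the SAP is not at hand. No size or direction of bias can be shown.

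**Conclusion.** The point holds as a minor drafting error in an operative safety instruction. The classification in 4.1.1 and the synopsis makes the stop in 3.5 and 6.4 wider than the rest of the protocol implies, and it does so mainly for the adverse-event, laboratory or illness trigger and for pregnancy, in subjects who then remain under follow-up to Week 24.

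Confidence in the textual reading is high. Confidence in the consequence for an individual subject is lower: it rests on the assumptions that a site follows the rule to the letter and does not prescribe metformin outside the study. How many subjects would be affected cannot be derived from the protocol.

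**What to change.** In 3.5, mirrored in 6.4, replace the stop sentence with: *Subjects MUST discontinue blinded saxagliptin/dapagliflozin/placebo; open-label metformin XR continues or stops at the investigator's discretion, and stops where the reason contraindicates it under the local label.* Leave 4.1.1 and the synopsis unchanged for drug accountability. Rescue medication needs no mention, because 4.1.2 treats it as noninvestigational and 3.5 already leaves it to the investigator.

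Do not pair this with a general permission in 3.4.1 for any glucose-lowering therapy after the blinded product stops. That would admit agents that the rescue rules exclude (GLP-1 analogs and other DPP4 or SGLT2 inhibitors). It would also let HbA1c under new therapy into a primary model whose only stated exclusion is data after rescue. If the sponsor does want to allow such therapy, the protocol should require the agent and start date to be recorded and should treat that start as rescue in the efficacy analyses.

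The core change costs wording in two places, the usual ethics review of an amendment under 9.1.1 and one site communication. Table 5.1 already reviews concomitant medication at every visit, so no visit or procedure is added. Limiting the stop rule to the blinded tablets needs no change to the analysis; the optional allowance of other therapy would need the rescue convention above.
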